9.5.6. Primary Endpoint

The International Council for Harmonisation of Technical Requirements for Pharmaceuticals for Human Use [ICH] E9 (R1) provides further information on estimands and sensitivity analyses in clinical trials; ICH E9 (R1) came into effect on 30 Jul 2020 and follows below.

Definition of the Estimand for the Primary Endpoint

- Population: adult participants with moderate to severe PV newly diagnosed or experiencing flare, on add-on therapy of low doses of oral prednisone, and that are further defined by the inclusion (Section 5.1) and exclusion (Section 5.2) criteria.
- Variable: proportion of PV participants who achieve CRmin within 30 weeks
- Main intercurrent events (ICEs):
 1. Intercurrent medications before CRmin
 - a. Immunosuppressants or dapsons at therapeutic doses for at least 4 weeks
 - b. IVIg at immunomodulating dose (≥ 1 g/kg/month)
 - c. Immunoabsorption or plasma exchange
 - d. Rituximab or other anti-CD20 biologics
 - e. IV corticosteroids >200 mg cumulatively within 2 weeks
 2. Discontinuation of IMP before CRmin due to lack of efficacy
- Population-level summary: the strata-adjusted difference in the proportion of responders (95% CI) between efgartigimod PH20 SC in combination with add-on therapy of low doses of oral prednisone and placebo in combination with add-on therapy of low doses of oral prednisone.

Handling of Main ICEs

A composite strategy approach will be taken to address both main ICEs. This implies that participants that take intercurrent medications before CRmin as specified previously, as well as participants that discontinue IMP before CRmin due to lack of efficacy, will be considered nonresponders for the primary endpoint analysis.

Estimation of Treatment Effect and Statistical Inference

The proportion of participants with PV having achieved CRmin within 30 weeks will be tested by means of a stratified Cochran-Mantel-Haenszel (CMH) test using the mITT population. The model will be stratified by disease status, disease severity, and body weight at randomization. The strata-adjusted difference of proportions will be presented with its 95% CI and 2-sided p-value. In addition, the odds ratio and its 95% CI will be provided.

Handling of Missing Data

Missing data for reason of 1 of the main ICEs will be handled as described above.

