9.5.7. Key Secondary Endpoints Subject to Alpha Control

The first key secondary endpoint, defined by the proportion of PV+PF participants that have achieved CRmin within 30 weeks, will be tested using a stratified CMH test with stratification variables similar as for the primary endpoint, using the mITT population. As this first key secondary endpoint is similar to the primary endpoint, the same approach for handling the main ICEs, as suggested for the primary analysis, will be applied.

The second key secondary endpoint, cumulative prednisone dose over the trial duration, will be analyzed in the form of a normalized cumulative prednisone dose (NCPD), normalizing by weight and by number of days in study and will be denoted as NCPD. The NCPD endpoint will be analyzed using the mITT population in PV participants. The following formula will be adopted to calculate NCPD for each participant.

$$\text{NCPD} = \frac{\text{Cumulative Prednisone Dose during the treatment period of the patient}}{(\text{Weight of the patient at baseline}) \times (\text{number of days treated})}$$

For the NCPD endpoint, the analysis of variance (ANOVA) model will be used to compare both treatment groups. The model will include treatment and the stratification variables will be considered as factors.

For the third and fourth key secondary endpoint, respectively time to CR and time to DC, both treatment groups will be compared using the Fleming-Harrington weighted log-rank statistic FH (1,0).⁴⁴ This analysis will be performed using the mITT population (PV participants). For both endpoints, survival curves will be estimated using the Kaplan-Meier time to event method.

Details on how to deal with the main ICEs for the second, third, and fourth key secondary endpoints will be provided in the SAP.

The primary endpoint will be tested at a 5% 2-sided alpha level and will act as a gatekeeper for testing the secondary endpoints. Subject to meeting significance for the primary endpoint, secondary endpoints will be tested at the 5% 2-sided significance level in a strict **hierarchical order** as follows:

1. Comparison of the proportion of PV+PF participants having achieved CRmin within 30 weeks between efgartigimod PH20 SC and placebo
2. Comparison of the NCPD in PV participants between efgartigimod PH20 SC and placebo
3. Comparison of time to CR in PV participants between efgartigimod PH20 SC and placebo

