4.1.2.1 PRIMARY ENDPOINT

The primary endpoint is the proportion of PV participants having achieved CRmin (as assessed by the investigator) within 30 weeks. A stratified Cochran-Mantel-Haenszel (CMH) test will be calculated with the stratification factors of disease status, disease severity, and body weight at randomization.

Disease activity relative day will be calculated as specified in Section 2.2.3. Any CRmin achieved with a relative day up to day 218 is counted as a primary endpoint response. CRmin cases achieved for the first time after day 218 will not be considered.

The main analysis on the primary endpoint will use the ‘composite strategy’ approach in case of main intercurrent events. This strategy implies that when a main intercurrent event (ICE) occurs, a participant is considered a non-responder. This happens in the following situations:

	Statistical Analysis Plan	
ARGX-113-1904	Final analysis	Final 2.0 of 22NOV2023

- Intercurrent medications (see section 3.4.2) before CRmin
 - Immunosuppressants or dapsone at therapeutic doses for at least 4 weeks in total in the last 12 weeks before achieving CRmin
 - IVIg/SCIg at immunomodulating dose (≥ 1 g/kg/month) before achieving CRmin
 - Immunoabsorption or plasma exchange (at least 1 procedure) before achieving CRmin
 - Rituximab or other anti-CD20 biologics (at least 1 infusion) before achieving CRmin
 - IV or IM corticosteroids administered (at least 1 administration, any dose) once the participant has achieved minimal prednisone (or prednisone equivalent) dose of ≤ 10 mg/day (i.e., during the 8 week period required in the protocol to confirm the CRmin status) or administered at any moment before achieving CRmin in any of the three following situations:
 - a) more than 60 mg for 3 consecutive days
 - b) more than 40 mg for 4 consecutive days
 - c) more than 7 days in total
 - Tetracyclines administered at least 100 mg/day for at least 2 weeks in total in the last 10 weeks before achieving CRmin
 - Any interventional study drug under development for pemphigus given before achieving CRmin
- Discontinuation of IMP before CRmin due to lack of efficacy
- Death

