- Intercurrent medications (see section 3.4.2) before CR: participant is assumed to not reach CR until the theoretical end of the study and is censored at day 218.
- Discontinuation of IMP before CR due to lack of efficacy: participant is assumed to not reach CR until the theoretical end of the study and is censored at day 218.

Participants without any disease assessment are censored at day 1. Participants with disease assessment but not achieving CR in the period from Day 1 to Day 218 and without intercurrent event in that period are censored at the earliest of day 218 and the end of treatment + FU phase.

A supplementary analysis for this secondary endpoint will use the ‘treatment policy strategy’ where the occurrence of the intercurrent event is considered irrelevant: Time to CR is calculated regardless of whether or not the intercurrent event occurs.

4) Time to DC in PV participants, calculated as the difference between the first date DC was achieved and the first IMP administration date. Similar calculations, ICE handling and censoring rules are applied as for ‘time to CR’ (composite strategy).

A supplementary analysis for this secondary endpoint will use the ‘treatment policy strategy’ where the occurrence of the intercurrent event is considered irrelevant: time to DC is calculated regardless of whether or not the intercurrent event occurs.

Both time to event endpoints will be statistically evaluated using the stratified Fleming-Harrington weighted logrank statistic FH (1,0), with the stratification factors disease status, disease severity, and body weight at randomization. For both, Kaplan-Meier survival plots by treatment arm will be produced (as in-text figures only).

5) NCPD over the whole planned treatment phase in all participants: same derivation as second key secondary endpoint (composite strategy and treatment policy strategy) but for all participants.

6) Time to DC in all participants: same derivation as fourth key secondary endpoint (composite strategy) but for all participants.

7) Time to CR in all participants: same derivation as third key secondary endpoint (composite strategy) but for all participants.

	
Statistical Analysis Plan
	

ARGX-113-1904
	
Final analysis
	
Final 2.0 of 22NOV2023

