6. CHANGES TO THE PLANNED ANALYSIS

6.1 CHANGES NOT COVERED BY PROTOCOL AMENDMENTS BEFORE DATABASE LOCK

Analysis visit labels deviate from the visit labels in the schedule of assessments of the protocol to accommodate the example in the ICH E3 guideline annex III.

NCPD, time to CR and time to DC for PV+PF participants are added to the fixed-sequence testing procedure.

NCPD (mg/kg/day) is calculated for different periods as [the sum of (equivalent doses taking into account daily dose frequency)/(body weight in kg)]/(period duration in days) with body weight of visit closest before or at each start of prednisone equivalent medication record instead of using weight at baseline.

The following extra analyses will be conducted, which are not covered in the clinical study protocol (CSP):

- Cox proportional hazard model on time to event endpoints
- Stratified Mann-Whitney test on NCPD and GTI endpoints
- Selected endpoints on the subset of PF participants

The following extra endpoints will be derived, which are not covered in the CSP (see section 4.1.2.3 and 3.5.2):

- Time to CRmin
- NCPD defined for different periods
- Cumulative prednisone dose (mg) over different periods
- Time to first flare for different periods
- Proportions of participants with DC/CR
- Duration of CRmin

The CSP pre-specified a list of medications whose use is to be considered an intercurrent event to be handled using the composite strategy. These medications were: immunosuppressants or dapsone, IVIg at immunomodulating doses, immunoadsorption or plasma exchange, rituximab or anti-CD20 biologics and IV corticosteroids. In this SAP, the following therapies, not mentioned in the CSP, have also been added as intercurrent events to be handled with the composite strategy: tetracyclines and any interventional study drug under development for pemphigus.

The following analysis, covered in the CSP, will not be performed since no comparable historical data are available for the control arm in the PF literature:

- The magnitude of the effect of efgartigimod PH20 SC compared to placebo in the PF subpopulation will be evaluated using the posterior distribution of the treatment effect (difference between efgartigimod PH20 SC and placebo) obtained in a Bayesian analysis. This Bayesian analysis will incorporate historical data for the placebo in an informative maximum a posteriori probability estimate prior with robustness modifier.

	Statistical Analysis Plan	

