9. APPENDICES

9.1 MAIN INTERCURRENT EVENTS (ICE)

The conditions below are tailored for the primary endpoint (CRmin). Conditions based on medication type, minimal dosing and minimal duration apply to the other endpoints with composite strategy or hypothetical strategy. However, conditions like “in the last 12 weeks before achieving CRmin” are specific for CRmin only. For these strategies, NCPD is calculated until and excluding the first day of ICE unless specified otherwise.

9.1.1 *Immunosuppressants or dapsone at therapeutic doses for at least 4 weeks in total in the last 12 weeks before achieving CRmin*

- Azathioprine, at least 1 mg/kg/day
- Mycophenolate mofetil, at least 2 g/day
- Mycophenolic acid, at least 1000 mg/day
- Mycophenolate mofetil hydrochloride, at least 2 g/day
- Cyclophosphamide, at least 1 mg/kg/day, or IV pulse 500 mg/month
- Methotrexate (sodium), at least 5 mg/week (in Japan), whereas 10 mg/week in Europe
- Ciclosporin, at least 3 mg/kg/day
- Dapsone, at least 1 mg/kg/day
- Hydroxychloroquine sulfate, at least 400mg/day
- Thalidomide, at least 50mg/day

For CRmin and time to CRmin these events should occur in the last 12 weeks before CRmin to be considered as an ICE. NCPD is calculated until and including the last day of the applicable 4 weeks intake.

9.1.2 *IVIg/SCIg at immunomodulating dose (≥ 1 g/kg/month) before achieving CRmin*

- ‘Immunoglobulins NOS’ or ‘Immunoglobulin G Human’ or ‘Immunoglobulins’ or ‘Immunoglobulin Human Normal’ or ‘Anti-D Immunoglobulin
and cmroute=’INTRA VENOUS’ or ‘SUBCUTANEOUS’.

9.1.3 *Immunoabsorption or plasma exchange (at least 1 procedure) before achieving CRmin*

- ‘Plasmapheresis’ or ‘Immunoabsorption therapy’ as PRDECOD, at least one cycle

	Statistical Analysis Plan	
ARGX-113-1904	Final analysis	Final 2.0 of 22NOV2023

9.1.4 *Rituximab or other anti-CD20 biologics (at least 1 infusion) before achieving CRmin*

- Rituximab, at least one cycle of 1 g or 375 mg/m²
- Obinutuzumab
- Ofatumumab
- Ocrelizumab
- Ibritumomab tiuxetan
- Veltuzumab
- Tocilizumab

9.1.5 *IV or IM corticosteroids*

- administered (at least 1 administration, any dose) once the participant has achieved minimal prednisone (or prednisone equivalent) dose of ≤ 10 mg/day (i.e., during the 8 week period required in the protocol to confirm the CRmin status) or administered at any moment before achieving CRmin in any of the three following situations:
 - a) more than 60 mg of prednisone equivalent for 3 consecutive days

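### Do time to CR and time to DC lack a censoring rule for death and for treatment-failure exits?

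*SAP*

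**What the plan says.** Protocol 9.5.7 leaves the rule to the SAP: "Details on how to deal with the main ICEs for the second, third, and fourth key secondary endpoints will be provided in the SAP". Protocol 9.5.6 names two main intercurrent events (ICEs) for the primary endpoint. One is a list of therapies; the other is "Discontinuation of IMP before CRmin due to lack of efficacy". Death is on neither.

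SAP 4.1.2.1 uses a composite strategy for the primary endpoint: "This strategy implies that when a main intercurrent event (ICE) occurs, a participant is considered a non-responder". Its list of situations ends with death. SAP 6.1 records that certain therapies "have also been added as intercurrent events to be handled with the composite strategy: tetracyclines and any interventional study drug under development for pemphigus"; it does not mention death.

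For time to CR, SAP 4.1.2.2 has two ICE bullets under the composite label. One covers intercurrent medication. The other reads "Discontinuation of IMP before CR due to lack of efficacy: participant is assumed to not reach CR until the theoretical end of the study". Both censor at Day 218. Participants with no disease assessment are censored at Day 1. The rest, if assessed, not in CR and "without intercurrent event in that period are censored at the earliest of day 218 and the end of treatment + FU phase", make up the residual group. For time to DC, "Similar calculations, ICE handling and censoring rules are applied as for" time to CR.

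SAP 9.1, where the reader is sent for ICE derivation, deals with medications and procedures only: "Conditions based on medication type, minimal dosing and minimal duration apply to the other endpoints with composite strategy or hypothetical strategy".

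**The concern.** Two things look unfinished.

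**Death.** If death is a main ICE for these endpoints because SAP 4.1.2.1 makes it one for CRmin, it has no bullet in 4.1.2.2. It is also shut out of the residual rule, which covers only participants with no ICE. On that reading a death before CR or DC has no date.

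**Lack of efficacy.** Treatment failure has three routes: no DC at the top prednisone step, an uncontrolled flare between DC and CRmin, and a prednisone-related SAE. Participants who fail may move early to the extension study. No passage says which of these exits is a stop for lack of efficacy. One that counts is held at Day 218; one that does not is censored at study exit. Participants who roll over have no follow-up phase, so their exit is the end of the treatment phase.

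These endpoints are steps 4, 5, 7 and 8 of the fixed sequence in SAP 4.1.4. One non-significant result stops everything after it, so a rule chosen after unblinding could matter.

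**Working it through.** **1. Which ICEs must 4.1.2.2 handle?** Protocol 9.5.7 asks for the main ICEs. Protocol 9.5.6 defines two, and SAP 4.1.2.2 handles the same two for time to CR. It uses the same two for the normalised cumulative prednisone dose just above. Death in SAP 4.1.2.1 is an extra line for the primary endpoint. For a death before CRmin it changes nothing, because a participant for whom CRmin was never recorded is already a non-responder there. It is weak evidence that death was meant to carry over.

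**2. Does a death then have a date?** Yes. The residual rule gives the earlier of Day 218 and the end of the treatment plus follow-up phases. SAP 2.2.1, Table 1, ends the last phase at study termination. A death with no disease assessment goes to Day 1.

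**3. Is lack of efficacy operational?** The ICE is a reason for stopping drug. SAP 3.1.1 takes treatment discontinuation and its reasons from the end-of-treatment page. Treatment failure is a separate investigator assessment (SAP 4.1.2.3, item 5). If the page has a lack-of-efficacy category, no mapping from failure routes is needed. The page is not in the documents, so this is an assumption. The derived failure reason in item 5 would be a poor substitute. It tests for absence of DC first, so a prednisone-SAE failure before DC would be labelled as no DC, although the definition of treatment failure puts no DC condition on that route.

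**4. Size.** The plan states no power for these endpoints, so there is no figure to reproduce. Inputs: 183 PV participants at 2:1 (SAP 1.3), so 183 × 2/3 = 122 and 61; weekly visits from Day 8 to Day 218; the FH(1,0) statistic:

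Z = Σ w(d₁ − d·n₁/n) / √[Σ w²·d·(n₁/n)(1 − n₁/n)(n − d)/(n − 1)], with w = S(t−).

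Assumed, not from the documents: exponential time to CR; CR by Day 218 of 75% vs 60%; deaths at weeks 4-26; failure exits at weeks 4-15. The test is unstratified, both rules are applied to the same trials, and each scenario has 10,000 trials. Rates are efgartigimod/placebo.

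| Scenario | Held to Day 218 | Censored at exit | Difference |
|---|---|---|---|
| Deaths 1%/1% | 51.1% | 51.4% | −0.3 |
| Deaths 1%/2% | 54.2% | 53.5% | +0.7 |
| Deaths 2%/1% | 49.5% | 51.3% | −1.8 |
| Failure exits, never remit, 2%/4% | 55.8% | 52.9% | +2.9 |
| same, 4%/2% | 43.7% | 48.7% | −5.0 |
| same, 5%/5% | 47.9% | 49.8% | −1.9 |
| Failure exits, unrelated to remission, 2%/4% | 54.0% | 51.3% | +2.7 |
| same, 4%/2% | 48.5% | 51.7% | −3.2 |
| same, 5%/5% | 50.1% | 50.8% | −0.7 |

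Deaths of 1%/2% are about one person per arm (122 × 0.01 = 1.2; 61 × 0.02 = 1.2). For time to DC (assumed medians 3.5 vs 5 weeks, deaths at weeks 2-6), 1%/1% gives 47.3% vs 48.4% and 1%/2% gives 51.3% vs 49.9%. A stratified version (8 equal strata, 4,000 trials) gives 50.2% vs 49.3% for deaths of 1%/2% in time to CR.

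The verdict at p<0.05 for time to CR differs between the rules in 1.7-2.6% of trials for deaths and 4.2-5.9% for failure exits at weeks 4-15. Those figures come from settings near 50% power, where verdicts change most easily. At 75% vs 50% CR (power about 90%, 2,500 trials) they fall to 0.3-0.5% for deaths and 1.3% for failure exits of 2%/4% unrelated to remission.

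**5. Does either rule protect type I error better?** One-sided error favouring efgartigimod at equal CR of 60% (20,000 trials), held vs at exit:

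- Exits unrelated to remission: 2%/4% gives 2.6% vs 2.1%; 4%/2% gives 1.8% vs 2.2%; 5%/15% gives 5.0% vs 2.3%.
- Exits drawn from non-remitters: 2%/4% gives 2.4% vs 1.8%; 4%/2% gives 2.2% vs 2.9%; 5%/15% gives 2.3% vs 0.6%.

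Neither rule is uniformly closer to 2.5%.

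**The case for a change.** The best case for a change is that the protocol handed this task to the SAP, the endpoints carry alpha, and the sign of the effect depends on which arm loses more participants. The section opens by referring to main ICEs under a composite label, and the subsection before it counts death among them. Two sentences using data already collected would settle it.

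Part of this stands. The SAP does not say in words whether death carries over, SAP 6.1 should have logged death as an addition for the primary endpoint, and the lack-of-efficacy reason is not spelled out. The failure-exit classification matters more than the death date: at an assumed 5% vs 15%, with CR of 70% vs 50% and exits on days 30-199, power is 77% held and 72% at exit.

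The rest does not amount to a fault. No stated rule is shown to give a wrong answer. Holding deaths at Day 218 is one defensible convention and the residual rule is another. Asking for a mapping of failure routes does not show that a recorded stop reason is inadequate. SAP 4.1.2.2 also specifies a treatment-policy analysis of both endpoints, which ignores the ICE and so leaves recorded lack-of-efficacy exits to the residual rule. That shows one side of the choice; it does not cover exits recorded under other reasons.

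**Conclusion.** No change to the plan follows. This is a gap in wording that an analyst fills sensibly, plus a clerical omission in SAP 6.1. On the plain reading a death before CR or DC is dated by the residual rule, and lack of efficacy is taken from the recorded reason for stopping drug. On the alternative reading a death is held at Day 218, which fits the composite label equally well. The two differ by 0.3 to 1.8 points of power for time to CR at assumed death rates of 1-2%.

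For failure exits of 2-5% the difference is 0.7 to 5.0 points in either direction, and neither rule is better across the null scenarios, so imposing one brings no clear gain. All event rates and CR rates are assumptions. The conclusion on lack of efficacy also assumes that the end-of-treatment page carries a usable reason, which the documents neither confirm nor contradict.

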4.1.2.3 OTHER SECONDARY ENDPOINTS (NOT ALPHA CONTROLLED)

All other secondary endpoints will be analyzed using the mITT population. Analyses related to data in the period after an event (CRmin, DC) can only be performed in participants with that event.

1. Proportion of PF participants who achieve CRmin within 30 weeks: same derivation as for the primary endpoint (composite strategy) but then for PF participants.
2. Time to CRmin in PV, PF and all participants: same derivation as third key secondary endpoint (composite strategy) but using date of achieving CRmin. Time to CRmin is defined as the time to the moment that the participant achieves CRmin status defined as complete remission while receiving prednisone therapy at 10 mg/day or less for at least 8 weeks, based on the assessment of the investigator. The 8-week period with minimal prednisone necessary to confirm CRmin is included as part of this time period. For example, a participant that achieves complete remission with prednisone ≤ 10 mg/day at week 15 for the first time and maintains this status for 8 weeks will have a time to CRmin of $15 + 8 = 23$ weeks.
3. Proportion of participants achieving DC in PV, PF and all participants (composite strategy)
4. Proportion of participants achieving CR in PV, PF and all participants (composite strategy)

For all subsequent secondary endpoints a treatment policy strategy is applied ignoring ICEs.

5. Proportion of treatment failures as assessed by the investigator in PV and in all participants. Specific reasons for treatment failure can be derived as follows in following order:
 - absence of DC: if participant didn't achieve DC as assessed by the investigator
 - prednisone related SAE: occurrence of an SAE after DC considered related to prednisone by the investigator
 - flare: if previous 2 reasons are not applicable, the reason must be a flare between DC and CRmin that is not controlled by a prednisone dose that is 2 dose levels above the dose at which the flare is observed and that is a least 0.3mg/kg qd

Failure is defined for the whole treatment phase.
6. Number of flares in PV and in all participants: count number of flares as assessed by the investigator. A new flare only emerges after a new DC. Number of flares are counted over the whole treatment + follow-up phase, between first DC and CRmin (or end of treatment period for participants without CRmin) and after CRmin. The initial flare at baseline (if applicable) is not counted.
7. Time to first flare from first DC in PV and in all participants is calculated as (visit date of flare)-(date of first DC)+1. Similarly time to first flare from first CR and time to first flare from CRmin will be calculated as (visit date of flare)-(date of first CR and date of CRmin respectively)+1.

	
Statistical Analysis Plan
	

ARGX-113-1904
	
Final analysis
	
Final 2.0 of 22NOV2023

8. Proportion of PV and all participants with at least one flare after DC. The same periods are considered as for number of flares: i.e. whole treatment + follow-up phase, between first DC and CRmin (or end of treatment period for participants without CRmin) and after CRmin.
9. Duration of CRmin in PV, PF and in all participants: count the number of weeks CRmin is maintained. I.e. participant remains without a lesion after CRmin and with prednisone equivalent dose ≤ 10 mg/day maintained and with PDAI activity score=0 maintained. The 8-week period with minimal prednisone necessary to confirm CRmin is included as part of this duration. Participant is censored at EoS if still on CRmin at end of treatment phase (or follow-up phase if applicable).
10. PDAI at each visit in PV and in all participants: PDAI activity subscores (mucosal, skin and scalp), PDAI activity score and PDAI total score are assessed by the investigator at each visit. Data after the first occurrence of an intercurrent event will also be used (treatment policy strategy). Missing data (intermittent as a result of the scattered way of data collection and non-intermittent as a result of study discontinuation), will be imputed using last observation carried forward (LOCF).
11. QoL in PV and in all participants: ABQOL (17 items) and EQ-5D-5L (i.e., mobility, self-care, usual activities, pain/discomfort, anxiety/depression and VAS) are assessed by the investigator at baseline, Week 4, Week 14 and at EoS. A total ABQOL score is calculated as the sum of all 17 items score 0 to 3 with higher score indicating worse condition. Missing items are imputed with the average score of the present items if at least half (9) of the items are present. The total score is rounded to the highest integer.
12. C-GTI in PV and in all participants: Composite Glucocorticoid Toxicity Index comprises the Aggregate Improvement Score (AIS) and the Cumulative Worsening Score (CWS) (health impact of GC) and is measured at baseline, Week 14 and EoS/ED. AIS and CWS are calculated for the first 14 week period (W14), for the last 16 week period (W30) and for the treatment phase overall (Overall). The last post-baseline assessment (Overall) is considered as the overall CWS/AIS and is calculated as a cumulative score over all post-baseline timepoints. The complementary GTI specific list (GTI-SL) will only be listed.

